## 1. Study Summary

Study Title	Randomized Controlled Trial To assess the Benefits of Dexcom Continuous Glucose Monitoring with Glucose telemetry System for the Management of Diabetes in Long-term Care Setting: The CGM-GTS in Long-term care
Study Design	Randomized Controlled Trial
Primary Objective	To compare differences in frequency of hypoglycemia (<70 mg/dl) and glycemic control (time in range [TIR] 80-180 mg/dl) between the Dexcom CGM with Glucose Telemetry System (CGM-GTS) compared to a standard of care protocol, in residents with T2D treated with insulin and/or insulin-secretagogues, in subacute and long-term skilled nursing care facilities.
Secondary Objective(s)	Determine differences in clinical outcomes (number of complications, ER visits and need for hospital re-admissions), and health care utilization between the use of real-time Dexcom CGM Glucose Telemetry System (CGM-GTS) compared to a standard of care in patients with T2D in subacute and long-term skilled nursing care facilities.
Research Intervention(s)/Interactions	POC testing or to real time Dexcom CGM with GTS for up to 60 days of admission.
Study Population	Adult residents with T2D in subacute and long-term skilled nursing care facilities treated residents with T2D treated with insulin and/or insulin-secretagogues.
Sample Size	100
Study Duration for individual participants	Length of admission to subacute and long-term skilled nursing care facilities or up to 60 days (whichever comes sooner)
Study Specific Abbreviations/ Definitions	T2DM: Type 2 Diabetes Mellitus OADs: oral antidiabetic medications CGM: continuous glucose monitor GTS: glucose telemetry system LTC: Long Term Care SSI: Sliding Scale Insulin
Funding Source (if any)	Dexcom, Inc.

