Recent studies from our group and others in hospitalized patients with T2D have reported increased detection of both hypo- and hyperglycemic events with the use of CGM compared to POC BG testing 21,23-25. We also reported that the hospital use of the Glucose Telemetry System with Bluetooth technology allows CGM glucose values to be transmitted from the patient's bedside to a central monitoring device in the nursing station, reducing the frequency of hypoglycemia in insulin treated patients with T2D 26,27. More recently, in collaboration with the University of Maryland, reported significant reduction in the rate of hospital hypoglycemia in insulin treated medicine and surgery patients with T2D using the glucose telemetry system with real-time CGM 28. In addition, the use of Dexcom G6 CGM in insulin-treated patients revealed great accuracy, with 98.6% of reading within Clarke error Grid A and B (unpublished data, see preliminary results section). Thus, our experience in the hospital supports the use of the use of CGM for the management of patients with diabetes and prevention of hypoglycemia. However, we do not know if this experience can be extrapolated to individuals in long-term skilled nursing facilities. Therefore, in-depth analyses of glycemic control and potential benefit of RT-CGM in real-world is needed to determine whether the CGM-GTS can improve glycemic control and prevent hypoglycemia in vulnerable population of adult patients admitted to LTC facilities.

The primary aim is difference between POC testing and CGM-GTS in the frequency of hypoglycemia (safety outcome) and glycemic control (efficacy outcome) during admission.

- 1) Hypoglycemia <70 mg/dl and clinically significant hypoglycemia <54 mg/dl (safety outcome)
- 2) Glycemic control, as measured by time in range (TIR) between 80-180 mg/dl (efficacy outcome)

[figure not shown]
**Secondary outcomes** include differences between groups in any of the following measures:

1. Nocturnal hypoglycemia < 70 mg/dl and < 54 mg/dl (between 22:00 and 06:00)
2. Number of hypoglycemia events (< 70 and 54 mg/dl)
3. Time in hypoglycemia (<70 mg/dl) and hyperglycemia (>240 mg/dl)
4. Number of prolonged hypoglycemia > 1 and 2 hours by CGM
5. Frequency and time of hypoglycemic during the day and night
6. Frequency and duration or time on hyperglycemia > 240 mg/dl
7. Percentage of BG readings within target BG of 70 and 180 mg/dl
8. Glycemic variability calculated by standard deviation and MAGE

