The present aims of this RCT is to investigate whether the Dexcom G6 CGM with Glucose Telemetry System (CGM-GTS) with hypoglycemia alarm may reduce the risk of hypoglycemia < 70 mg/dl (safety outcome) and improve glycemic control as measured by the percent of time in range (TIR) 70-180 mg/dl (efficacy end-point) in patients with T2D in subacute and long-term skilled nursing care facilities. Patients in the standard of care group will wear a blinded CGM and receive POC testing before meals and bedtime, with providers adjusting oral agents or insulin dose based on POC results. Patients in the intervention CGM group will have a single daily fasting POC testing and will wear a real-time Dexcom G6 with GTS, and providers will adjust oral or insulin therapy based on CGM-GTS profile information. [name], PhD at the School of Public Health at Emory University will conduct statistical analyses.

For the safety endpoint, we will first compare the proportions of patients who have at least one episode of hypoglycemia by POC and by CGM. We will first perform nonparametric comparisons of the rate of hypoglycemia based on a two-sided Chi-square test (or Fisher's exact test in the presence of low incidence rates), followed by the Cochran-Mantel-Haenszel test, which adjusts for the potential center effect. Then we will perform univariate Poisson regression (or Negative Binomial regression) to assess whether there is any difference in the number of clinically significant hypoglycemia events between the two treatment groups. We will further conduct multivariate Logistic regression, Poisson regression (or Negative Binomial regression) to estimate the difference in the rate and frequency of hypoglycemia while adjusting for potential confounders. A glucose value < 70 mg/dl is considered as hypoglycemia requiring a nurse-driven response; thus, a BG <70 mg/dl will be used for sample size calculation. Data from Singh et al a reduction of hypoglycemia was reported comparing the CGM/GTS system than POC (Singh et al 2020) per patient (0.67 episodes per patient, 95% CI 0.34-1.30

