versus 1.69 episodes per patient, 95% CI 1.11-2.58,  $p= 0.024$ ) . Based on the results of the recent glargine U100 vs U300 study using CGM monitoring in the hospital, 56% had CGM BG readings <70 mg/dl (vs 14% with POC testing-standard of care), it is reasonable to assume 60% of resident on LTC facilities will experience one or more BG < 70 mg/dl by CGM. If we assume that 35% in the standard of care group will have at least one BG <70 mg/dl (based on linagliptin LTC study) , using one-sided, two-sample t-tests, we require we will need 70 patients per group to achieve 80% power.

Hypoglycemia incidence, Rate in the CGM intervention group	30%	35%	40%	45%	50%
Estimated sample size (N/group) for 80% power	49	70	107	186	407

For the efficacy endpoint, we will compare mean daily glucose levels measured by CGM or POC, and percent TIR measured by CGM between treatment groups by nonparametric Wilcoxon-tests or two-sample t-tests, and by multivariate linear regression, which adjusts for other potential confounders such as age, gender, BMI, center, and admission HbA1c. A logarithm transformation may be employed to make the data better conform to the normality assumption. When conducting multivariate regression analyses, we will apply standard variable selection and model checking procedures to decide the final model. Stepwise, backward, or forward model selection strategy will be adopted to determine the variables to be included in the final model. Standard diagnostic and model checking procedures, such as deviance residual plot and Hosmer- Lemeshow test, will be applied to examine the fit of the developed models. To show non-inferiority between POC and CGM in terms of glycemic control, we set the equivalence margin of 18 mg/dl (1 mosm/l), from a view that a difference <18 mg/dl is usually not considered as clinically significant . Based on the results from our recent CGM trials , it is reasonable to assume the standard deviation of mean daily BG is bounded above by 45 mg/dl. Assuming the true BG difference between the treatment groups is zero, and using one-sided, two-sample t-tests, we require 70 subjects for each treatment group to achieve 80% power.

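### Primary efficacy is TIR 80-180 mg/dl in Sections 1 and 4 but TIR 70-180 mg/dl in Section 18, and the only efficacy sizing is for non-inferiority of mean daily glucose

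*Combined protocol and SAP*

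**What the plan says.** Three current places in the combined protocol and SAP define the efficacy measure.

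- Section 1 (Study Summary), primary objective: "glycemic control (time in range [TIR] 80-180 mg/dl".
- Section 4 (Study Endpoints), second primary outcome: "Glycemic control, as measured by time in range (TIR) between 80-180 mg/dl (efficacy outcome".
- Section 18, under data management and statistical analysis: "improve glycemic control as measured by the percent of time in range (TIR) 70-180 mg/dl (efficacy end-point".

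Section 4 frames the comparison as a difference: "The primary aim is difference between POC testing and CGM-GTS in the frequency of hypoglycemia (safety outcome) and glycemic control (efficacy outcome) during admission".

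For the efficacy endpoint, Section 18 then says "we will compare mean daily glucose levels measured by CGM or POC, and percent TIR measured by CGM between treatment groups", by Wilcoxon or t-test and by linear regression. No TIR range is given there. It adds that "A logarithm transformation may be employed to make the data better conform to the normality assumption".

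The efficacy sample size follows: "To show non-inferiority between POC and CGM in terms of glycemic control, we set the equivalence margin of 18 mg/dl". The SD of mean daily glucose is taken as at most 45 mg/dl, and "Assuming the true BG difference between the treatment groups is zero, and using one-sided, two-sample t-tests, we require 70 subjects for each treatment group" for 80% power. Alpha is not stated. Hypoglycemia is sized separately in the same section. Sections 1 and 12 give a total of 100 participants.

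**The concern.** The plan leaves open two things that should be fixed before anyone sees data.

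The first is the range. Section 15 defines hypoglycemia as below 70 mg/dl. Time at 70-79 mg/dl therefore counts as efficacy success under 70-180. Under 80-180 it is neither in range nor a safety event. This is the part of the scale on which the intervention acts, because the alarm in Section 6 is set below 85 mg/dl. One CGM record thus gives two primary results, and an analyst working from Section 18 would not compute the outcome declared in Section 4. Section 19 plans interim analyses of the primary endpoint, so the ambiguity carries into those as well.

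The second is the variable and the hypothesis. The stated aim is to improve TIR, or to show a difference in it. The sizing is for showing that mean daily glucose is not worse by 18 mg/dl. Mean daily glucose is not among the primary or secondary outcomes in Section 4. A met margin could be reported as the efficacy result although it says nothing about whether TIR improved.

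**Working it through.** **1. The range.** For each participant, percent time at 70-180 equals percent time at 80-180 plus percent time at 70-79. Taking arm means and subtracting:

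effect on TIR 70-180 − effect on TIR 80-180 = between-arm difference in mean percent time at 70-79 mg/dl.

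- Time moved from 70-79 up to 80-180 raises only TIR 80-180.
- Time moved from below 70 up to 70-79 raises only TIR 70-180.
- One percentage point is 0.01 × 1440 = 14.4 minutes per day.

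The documents give no time at 70-79 by arm, so the size cannot be computed. With a Wilcoxon test or a log scale, both of which are allowed, the results still differ but not by this simple amount.

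Two other passages do not settle the matter. Secondary outcome 7 in Section 4 uses 70 and 180, but for the percentage of BG readings. The 80-180 range in Section 6 (Diabetes Management Protocol) is a treatment target, not an outcome definition.

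**2. The plan's own efficacy figure.** Inputs from Section 18: margin 18 mg/dl, SD 45 mg/dl, true difference 0, one-sided two-sample t-test, 80% power, 70 per group. Assumed here: one-sided alpha of 5% or 2.5%, and equal arms.

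Normal approximation: n per group = 2 × (z₁₋α + z₀.₈₀)² × (45/18)².

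- One-sided 5%: 2 × (1.645 + 0.842)² × 6.25 = 77.3, so 78. The noncentral t also gives 78.
- One-sided 2.5%: 2 × (1.960 + 0.842)² × 6.25 = 98.1, so 99. The noncentral t gives 100.

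Neither reproduces 70.

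**3. Power delivered.** The standard error is 45 × √(2/n), the noncentrality is 18 divided by the standard error, and there are 2n − 2 degrees of freedom.

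| n per group | Standard error | Noncentrality | Power, one-sided 5% | Power, one-sided 2.5% |
|---|---|---|---|---|
| 70 | 7.61 | 2.37 | 76.1% | 65.2% |
| 50 (total 100) | 9.00 | 2.00 | 63.4% | 50.8% |
| 78 | 7.21 | 2.50 | 80.0% | 69.9% |
| 100 | 6.36 | 2.83 | 88.0% | 80.4% |

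At 70 per group, 80% power would need a one-sided alpha of about 6.5%, or an SD of about 42.6 at one-sided 5% (37.7 at 2.5%). At 50 per group it would need an alpha of about 12.5%.

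**4. The total.** 2 × 70 = 140, against 100 in Sections 1 and 12.

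**5. TIR.** With no SD in the documents, the detectable difference can only be given in SD units. At two-sided 5% and 80% power it is 0.566 SD at 50 per arm and 0.477 SD at 70 per arm. As an illustration, with an assumed TIR SD of 15 to 30 percentage points:

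- 50 per arm: 0.566 × 15 = 8.5 to 0.566 × 30 = 17.0 points.
- 70 per arm: 0.477 × 15 = 7.2 to 0.477 × 30 = 14.3 points.

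**The case against.** The strongest reply is that the intent can be read from the plan. Both endpoint-defining sections say 80-180, the treatment target matches, and a 70-180 measure is already listed as secondary, so Section 18 may be a drafting slip. That supports 80-180 as the smallest edit. It does not remove the conflict, because Section 18 explicitly attaches the endpoint label to 70-180 and is the text an analyst will follow.

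Second, Sections 1, 4 and 18 each name TIR and no other variable as efficacy, so the priority between TIR and mean glucose is less open than it looks. This is fair as far as the labels go. Yet the analysis paragraph on the efficacy endpoint puts mean daily glucose beside TIR without ranking them, and sizes only mean glucose.

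Third, 45 mg/dl is offered as an upper bound. An SD of 42.6, about 5% lower, restores 80% at 70 per group if alpha is one-sided 5%. That is correct, but the stated 70 is tied to 45. The bound does not rescue 50 per group either, where the SD would have to fall to about 18 / (0.2 × 2.487) = 36.2 mg/dl (normal approximation) at one-sided 5%.

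Fourth, control patients also receive carbohydrate when a POC value is below 80 mg/dl, so both arms act near 70-79. This stands, and it may shrink the between-arm difference. Control POC testing is only before meals and at bedtime, so the difference need not vanish.

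Fifth, nothing shows that the range would change a conclusion. This also stands. The nearest figure, from the hospital telemetry trial described in Section 3, is 1.88 − 0.40 = 1.48 points of time below 70 (1.48 × 14.4 = 21 minutes per day). That is a different band and setting, so it gives context only.

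Finally, 140 against 100 is a separate defect that also touches the hypoglycemia sizing. It appears here because it sets the efficacy power actually delivered.

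**Conclusion.** The concern holds, and it must be fixed. The range conflict and the absence of any TIR sizing are established by reading the plan and need no calculation. The numerical effect of the range choice is unknown.

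The mean-glucose sizing does not deliver its 80%. The shortfall at 70 per group is 4 percentage points at one-sided 5% and 15 at one-sided 2.5%. At the stated total of 100 it is 17 and 29 points. Reaching 80% needs 156 or 200 participants in total.

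These figures rest on the plan's margin, SD and zero true difference, with no allowance for dropout. Alpha and 1:1 allocation are assumptions, because the sizing text gives neither.

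**What to change.** Before any data review:

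- State one CGM TIR range in Sections 1, 4 and 18, with a reason, and report the other as a labelled secondary outcome. Keeping 80-180 is the smallest edit, since it changes only Section 18.
- State that CGM TIR decides efficacy and is tested for a difference, as the aim requires.
- Label mean daily glucose as a separate non-inferiority analysis with a stated alpha, and say that meeting its margin will not be reported as improved TIR.
- Say that the existing efficacy sizing applies to mean daily glucose only. Reconcile 70 per group with the total of 100, and restate the power actually delivered.
- Give the TIR detectable difference as about 0.57 SD at 50 per arm (0.48 SD at 70), with any SD marked as an assumption.

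This concerns the outcome definition only. It leaves the treatment target and alarm settings alone.

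The cost is protocol and SAP wording plus a revised power statement. Both arms wear CGM, so either range can be computed from data already being collected. Enrolment may change if the sponsor keeps 80% power when reconciling the two sample sizes.

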## 5. Study Intervention/Investigational Agent

We propose to conduct a randomized controlled trial to determine whether compared to standard of care using capillary POC testing, the use of Dexcom CGM with Glucose Telemetry System (CGM-GTS) with hypoglycemia alarm will facilitate diabetes treatment and reduce the risk of hypoglycemia in insulin and non-insulin treated patients with T2D in LTC facilities.

Dexcom CGM- Glucose Telemetry System CGM-GTS). The system will include 3 main devices, i) DEXCOM G6 CGM device (sensor, transmitter, ii) a smart phone, and iii) a tablet computer located at the nursing station. As a first step glucose values obtained from the CGM sensor will be sent to the CGM transmitter by

Bluetooth technology and DEXCOM Share2 software application to a smart phone that serves as an intermediate-transmitting (routing) device. The study phone will be locked in a safe box located in the patient's room. With the help of commercial internet wireless network, glucose values from the smart phone will be transmitted wirelessly to a table computer (I-Pad) using the DEXCOM Follow application [<https://www.dexcom.com/apps>].

## 6. Procedures Involved

Residents with T2D in subacute and long-term skilled nursing care facilities treated with insulin and/or insulin-secretagogues will be randomized to a standard of care group with POC testing or to real time Dexcom CGM with GTS for up to 60 days of admission.

Patients in the standard of care group will wear a blinded CGM and receive POC testing before meals and bedtime, with providers adjusting oral agents or insulin dose based on POC results. Patients in the intervention CGM group will have a single daily fasting POC testing and will wear a real-time Dexcom G6 with GTS, and providers will adjust oral or insulin therapy based on CGM-GTS profile information.

Nursing staff and primary care will receive education on the CGM technology by our research team.

Education efforts will include general information on the technology, how and when to remove or replace CGM sensors and transmitters, and the hypoglycemia prevention protocol. Treatment of hypoglycemia (POC <70 mg/dl) will be similar in both groups following a standard hospital protocol.

[figure not shown]
CGM alarm settings, and prevention of hypoglycemia protocol. Hypoglycemia alarm will be set to < 85 mg/dl (for prevention for low blood glucose levels). Nursing staff will be instructed to provide 15 grams of carbohydrates in response to a hypoglycemia alarm. For control group (blinded CGM) CGM alarms are turned off, however if the POC is found to be between <80 mg/dl by POC, 15 grams of carbohydrates will be given as a preventive measurement for hypoglycemia (standard of care).

The hyperglycemia alarm will be set at 300 mg/dl. If this occurs, the nursing staff will assess clinical status and perform a POC glucose testing to confirm glucose values. If BG > 300 mg/dl, nursing staff will communicate the high glucose value to the primary care team.

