9. Number of sensor removal for procedures/imaging, sensors failures, sensors dislodgments

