## 19. Provisions to Monitor the Data to Ensure the Safety of Participants

Baseline and daily information will be entered by the study coordinators into data collection paper forms and into an electronic database (REDCap) provided by the Emory Research Information Technology Department. Baseline data will include demographics/history form (subject gender, age, ethnicity, type of treatment and comorbid conditions, body weight, BMI, laboratory results). Daily information will be collected on treatment, nutrition, blood glucose and laboratory values, complications and adverse events (hypoglycemia). The safety of interventions and treatments associated with this protocol will be under continuous review by

the investigative team. All adverse events will be reviewed bi-weekly in a multidisciplinary format that will involve review by a physician, and other members of the research team. All Serious Adverse Events will be reviewed within the applicable guidelines and submitted to the IRB and other appropriate regulatory bodies governing this study.

In addition, we have implemented protection against risks approaches as above to minimize the risk to our subjects.

**Stopping Rules:** We plan to perform interim analysis on the primary endpoint every 6 months and/or when half of the subjects have been randomized. The trial will be stopped if there is evidence beyond a reasonable doubt of a difference in the rate of death and hospital complications (two-sided alpha level, <0.01) between the treatment groups.

Plans for transmission of temporary or permanent suspension actions:

Any actions that mandate temporary or permanent suspension of study will be transmitted to the Emory IRB, and, if appropriate, to the FDA.

The frequency of protocol review will be: every 6 months.

The PI will forward reports of safety reviews within 15 days of the meeting to the Emory IRB.

See full Data safety monitoring plan in the attachment labeled Data Safety Monitoring Plan  
A Data Safety Monitoring Board or Safety Officer has been designated for this study.

[name]  
Department of Medicine/Endocrinology

[name], MPH  
Department of Medicine/Endocrinology

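### Blinded control sensors have no stated check, wear rule or wear-time offset, so unequal CGM capture could bias the hypoglycemia comparison toward no difference

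*Combined protocol and SAP*

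**What the plan says.** Section 5 sends CGM-arm values by phone to "a tablet computer located at the nursing station". Section 6 describes the control arm: "Patients in the standard of care group will wear a blinded CGM and receive POC testing before meals and bedtime". On scheduled fingersticks in the other arm it says: "Patients in the intervention CGM group will have a single daily fasting POC testing". Under the alarm settings and hypoglycemia prevention text it adds: "For control group (blinded CGM) CGM alarms are turned off". Staff education in the same section covers "how and when to remove or replace CGM sensors and transmitters", with no limit to one arm.

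For the safety endpoint, the statistical text in section 18 states that "we will first compare the proportions of patients who have at least one episode of hypoglycemia by POC and by CGM". Poisson or negative binomial models for event counts follow. No minimum wear, exposure offset or rule for missing CGM data is given there.

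Section 19 lists the daily data: "Daily information will be collected on treatment, nutrition, blood glucose and laboratory values, complications and adverse events (hypoglycemia". Sensor status is not among them. Section 4 lists as a between-group secondary outcome (number 9): "Number of sensor removal for procedures/imaging, sensors failures, sensors dislodgments".

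**The concern.** An any-event proportion and a raw event count both depend on how long each resident was observed. Time without CGM readings contributes no CGM-detected events, and without an exposure term it is treated as event-free.

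The arms differ in how easily a stopped sensor is noticed. A CGM-arm sensor that stops leaves a gap on a screen that nurses use for care. A blinded control sensor that stops while still on the skin gives no such sign, and the visible text puts no other check in its place. Follow-up of up to 60 days leaves room for several sensor sessions.

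Two results are exposed. The CGM-based safety comparison would lose control events and so understate any benefit of the intervention. The comparison of sensor failures (secondary outcome 9) would reflect partly how failures are found and not only how often they occur. Readings never taken cannot be recovered after the trial.

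**Working it through.** **Inputs from the documents**
- Any glucose below 70 mg/dl by CGM: 60%, used here as the control rate (section 18).
- Comparison rate: 35%, used here as the CGM-arm rate. The sample-size table heading gives it to that arm; the sentence before the table gives it to standard of care.
- Events per patient below 70 mg/dl in the earlier telemetry trial: 0.67 with telemetry, 1.69 with POC.
- Total of 100 participants, so 50 per arm if allocation is 1:1.

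**Assumptions**
- Two-sided alpha of 0.05.
- Control loses a fraction L of its CGM time; the CGM arm loses none. The documents give no value for L. One route to it: a fraction f of sensors fails at a uniformly random point and each gap lasts to the next scheduled change, so L = f/2. For f = 10%, 20%, 30%, L = 5%, 10%, 15%.

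**Step 1. The plan's own figure.** For 60% versus 35%, 80% power, two-sided 0.05 with continuity correction, the two-proportion formula gives 70 per group, as the table states. This does not depend on CGM capture.

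**Step 2. Observed control proportion, constant event rate.** Observed = 1 − (1 − 0.60)^(1−L).
- L = 5%: 1 − 0.4^0.95 = 58.1%
- L = 10%: 1 − 0.4^0.90 = 56.2%
- L = 15%: 1 − 0.4^0.85 = 54.1%

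**Step 3. The same with clustered events.** Let residents' event rates follow a gamma distribution with shape k. The mean m that yields 60% is m = k[0.4^(−1/k) − 1], and observed = 1 − [1 + m(1−L)/k]^(−k). For k = 1, m = 1.5, and L = 5% gives 1 − 1/(1 + 1.5 × 0.95) = 58.8%.

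**Step 4. Power.** Exact unconditional power of the Pearson chi-square test, 50 per arm, against 35%. With no loss it is 73.4%.

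| Control loss L | Constant rate: observed, power | k = 1: observed, power | k = 0.3: observed, power |
|---|---|---|---|
| 5% | 58.1%, 66.7% | 58.8%, 69% | 59.4%, 71% |
| 10% | 56.2%, 59.1% | 57.5%, 64% | 58.8%, 69% |
| 15% | 54.1%, 50.7% | 56.0%, 59% | 58.1%, 67% |

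If the CGM arm loses half as much as control (constant rate), power is 69%, 65% and 59%.

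**Step 5. Event counts without an offset.** The full-capture ratio is 0.67/1.69 = 0.396. The observed ratio is 0.396/(1 − L), giving 0.42, 0.44 and 0.47. The same factor applies at any glucose threshold, including the 54 mg/dl events named for the univariate count model.

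**Step 6. Percent-time measures.** Time in range and percent time below 70 mg/dl have captured time as their denominator. They are not biased if the loss is unrelated to glucose.

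**The case against.** A reader might infer from the alarm sentence that control sensor failures do go unnoticed, that control will lose more CGM time, and that hypoglycemia will be under-counted there. The documents do not establish any of these.

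- The sentence sits among the glucose alarm thresholds. Nothing says whether signal-loss or sensor-failure alerts are off in the control arm.
- Replacement training is not restricted to one arm, sensor failures are to be compared between groups and so must be recorded in both, and a dislodged sensor can be seen without a display.
- The transmitter stores as well as transmits data (section 15), so a lost transmission is not necessarily lost data.
- Control has more scheduled POC tests, which may catch some lows during a gap, so a net under-count across both methods is uncertain.
- A figure in section 6 and the separate data safety monitoring plan are not visible, so a sensor check may be written there.
- The constant-rate power figures are a worst case: they combine full loss in control with none in the CGM arm.

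These points stand, and they make the concern conditional. They do not close the gap. Training does not reveal that a blinded sensor still on the skin has stopped, and storage cannot recover readings that were never made. POC is not an equal substitute: its schedule differs by arm, and section 3 says it misses about 40% of hypoglycemia cases, particularly at night.

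**Conclusion.** The concern holds in conditional form. The arms differ in the visibility of sensor output, the CGM-based any-event proportion and the raw counts depend on captured time, and the visible text has no control sensor check, wear rule or wear-time offset. If control capture is lower, these two analyses are biased toward no difference, and detection of sensor failures differs by arm. Whether capture will differ, and by how much, cannot be known from the documents.

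Under the assumed control losses of 5–15%, the 60% rate is observed as 54–59%. Power drops by about 2 points at the mildest (5% loss, strongly clustered events) to about 23 points at the worst (15% loss, constant rate). The 73% starting point itself reflects 50 per arm against the 70 per group calculated, which is a separate matter. It would be too strong to say that sensor-failure data become uninterpretable: a control failure found at a sensor change or data download can still be counted, mainly with delay. The time-in-range outcome is not affected if the loss is unrelated to glucose.

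**What to change.** **Section 6.** State that in both arms the coordinator, during the existing daily data collection, confirms that the sensor is attached and its session active, without revealing control glucose values. Set one replacement window for both arms and log sensor on and off times.

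**Section 18.**
- Use log(valid CGM time) as the offset in the Poisson or negative binomial models.
- Report the percent of expected CGM time captured, by arm.
- An offset in the count models does not repair the chi-square and Cochran-Mantel-Haenszel comparison. Support it with a sensitivity analysis that accounts for captured time, for example a complementary log-log model for any event with a log valid-CGM-time offset.

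**Cost.** Brief coordinator time, one more CRF field and a few more control-arm sensors. No treatment rule changes. If capture proves equal, the log shows it and makes secondary outcome 9 easier to interpret.
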